### **Lab Check (Week 18 ± 3 days)**

During this study, the patient will have a sirolimus level checked for safety monitoring. This level can be drawn remotely.

### **Phone Visit (Week 20 ± 7 days)**

During this visit a study coordinator will contact the patient and review the interval history in detail. A report of any adverse events will be assembled in detail, along with a review of their concurrent medications. Any concerns brought up during this phone call will be reviewed with the investigator. In addition, sirolimus level for safety monitoring will be drawn at this visit. The sirolimus level can be drawn remotely.

### **Visit 4 (Week 24 ± 7 days)**

During this visit, the following will be performed:

- Obtain a urine pregnancy test for women of childbearing potential
- Obtain a urinalysis
- Review current medications
- Review the interval medical history, and perform a physical examination
- Perform spirometry after supervised administration of bronchodilator in the pulmonary function laboratory. [L1]  
[SEP]
- Perform DLCO in the pulmonary function laboratory
- Quality of life, dyspnea and fatigue assessments
- Obtain blood for CBC, CMP, lipid panel, VEGF-D measurement and sirolimus level; if the patient has consented obtain an additional sample to be stored on-site for potential future use
- Review drug diary and any reported adverse events
- Advise women of childbearing potential that they should continue to use their method of birth control for at least 4 weeks after the study ends

- Remind patients they will be contacted via phone in 4 weeks as a follow up
- Remind patients to follow up with their regular physicians for routine care

If at visit 4, it is determined there has been clinical benefit, the patient and her regular physician will decide how to proceed after the conclusion of the clinical study.

#### **End of study telephone call (Week 28 ± 7 days)**

An end of study phone call will be conducted at 4 weeks ± 7 days after the last study visit. The purpose of the call is to follow up on any open or unresolved adverse events.

#### **6.4 Enrollment**

Enrollment in the study will continue until the enrollment target of 25 patients is reached. This research study will be explained in lay terms to each potential research participant. The potential participant will sign an informed consent form before undergoing any screening study procedures. Participants who are deemed eligible for the study (see sections 6.1 through 6.3) at each of the study sites will be enrolled and assigned a unique participant ID number.

#### **6.5 Patient retention and drug compliance**

Patient retention will be encouraged in several ways. Extensive contact information will be captured for each patient, at the time of study enrollment. This will include home, work, and cellular telephone numbers and that of an emergency contact or nearest family member. Prior to each study visit, the study staff will contact the patient to remind her about the upcoming study visit. A check for the reimbursement of expenses up to \$500 will be issued after each study visit.

The study staff and physician will explain the importance of compliance with the study protocol at each patient contact. If a patient fails to comply with a study visit, the study staff will contact her by telephone. If the study staff is unsuccessful in reaching the patient, a follow up letter will be sent by overnight carrier, on two consecutive weeks, seeking follow-up.

Compliance with the protocol and drug administration will be strongly emphasized. Pill counts will be performed at visits and episodes of medication noncompliance will be recorded, including the reason for noncompliance. Patients will receive a calendar to document medication and any side effects experienced that day. If a patient wishes to withdrawal from the treatment phase of the study or has a serious adverse event (SAE) (whether related to study drugs or not), patient follow-up assessments will continue for safety monitoring and to avoid problems associated with missing data. The inclusion of such follow-up data will allow for analysis by intention-to-treat.

If a patient is withdrawn from study drug exposure for any reason, the patient will be strongly encouraged to continue with and complete the remainder of the study assessments, as scheduled.

## **6.6 Consent for future contact**

During the consent process, patients will have the option to provide permission for future contact. This permission allows for patient contact information, including their full name, address and telephone number, to be retained. The permission for future contact allows for possible patient re-contact regarding future IRB-approved studies. If the patient denies permission, no future contact will be made.

## **6.7 Consent for continuing data review of medical records**

During the consent process, patients will have the option to provide permission for future data review of their medical records. This permission allows for study staff to contact the patient (or the patient's caregiver(s)) to obtain medical records and other information for a period of up to two years after the patient has withdrawn from or completed the study. The purpose of this data review is to capture information including but not limited to clinical, radiographic, pathologic, laboratory and pulmonary function data, after the patient has exited the study. The rationale for future data review is that there may be long term effects of study treatment that are unknown to the investigators at this time.

## **6.8 Consent for storage of blood samples for future use**

Patients will be asked to consent to the storage of leftover blood and serum samples for future use related to LAM. Patients can refuse without impacting their care or ability to participate in this study.

## **6.9 Consent for participation in the home spirometry substudy**

Patients will be asked to consent for participation in the home spirometry evaluation, being done in conjunction with the clinical trial. Patients can refuse to participate in the home spirometry evaluation without impacting their care or ability to participate in this study.

## 7. Stopping rules

### 7.1 Participant withdrawal criteria

Participants may be terminated early from the study for the following reasons:

- a. The participant elects to withdraw consent from all future study activities, including follow-up.
- b. The participant is “lost to follow-up” (i.e., no further follow-up is possible because attempts to reestablish contact with the participant have failed).
- c. The participant dies.
- d. The participant develops a medical condition or is started on new medication(s) not previously mentioned in the list of prohibited medications that, in the opinion of the investigator, may pose additional risks from participation in the study, may interfere with the participant’s ability to comply with study requirements or that may impact the quality of the data obtained from the study.
- e. The participant is listed for transplant and is required to stop sirolimus therapy.
- f. In the opinion of the investigator, it is not in the participant’s best medical interest to continue to participate in the study.
- g. The participant meets any of the individual stopping rules as delineated in section 13.1.

### 7.2 Criteria for terminating the study

Up to 25 patients will be enrolled in this study. The maximum duration of patient participation is up to 28 weeks, including a follow-up phone contact 4 weeks after the last study visit. In the event of any death, or Grade IV Serious adverse event (SAE) attributable to the study agent and unexpected, enrollment will be suspended, pending Data Safety Monitoring Board (DSMB) review.

## **8. Study variables and measuring methods**

### **8.1 Physical Exams:**

Exams will be performed in a routine manner, consistent with the standard of care.

### **8.2 Pulmonary function testing**

Pre and post bronchodilator spirometry and DLCO measurement will be performed in a standardized manner according to American Thoracic Society/European Respiratory Society criteria for acceptability and repeatability (38). The study site will attempt to have the same respiratory therapist administer testing to patients for consistency in the study. All PFTs obtained as part of the study will be performed post bronchodilator only, regardless of whether bronchodilator responsiveness is demonstrated. All spirometry data will be assessed for quality by spirometry standardization expert and study investigators, [name], [name], and [name].

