Study Procedures	
The primary objective of this trial is to evaluate the change in serum VEGF-D after 24 weeks of combined resveratrol and sirolimus as compared to the baseline serum VEGF-D value on sirolimus alone. Secondary objectives include an assessment of the safety and tolerability of resveratrol in combination with sirolimus in patients with LAM, as well as the effect of combined resveratrol and sirolimus on lung function and quality of life. The frequency, severity and duration of all adverse events, regardless of cause, will be tabulated by body system and by severity using the NCI Common Terminology Criteria for Adverse Events v4.0. Subjects will have a medical history, physical examination, and laboratory measurements of complete blood count, renal and liver function tests, serum VEGF-D, and sirolimus levels drawn at every in-person visit. Pre and post bronchodilator spirometry measurements will be performed at each visit. St. George's respiratory questionnaire (SGRQ), SD-SB, EuroQOL and ATAQ LAM will be used for quality of life assessment, and these questionnaires will be filled out at each in-person study visit.
 
Patients enrolling in RESULT will be trained on proper technique for home spirometry using an advanced vertical turbine based device that records and wirelessly transmits full flow volumes loops. Once a week, patients will perform at least three spirometry maneuvers that pass ATS/ERS acceptability criteria and choose the best value as their weekly FEV1 and FVC. All spirometric data will be reviewed by an expert pulmonary physiologist, who will judge the spirometry data and loops for intra-test acceptability and reproducibility as specified in the ATS/ERS guidelines, as well as provide near real time electronic feedback to patients regarding their technique. We will correlate spirometry values and trends (absolute as well as rate of decline) obtained from weekly home spirometry with the office-based spirometry values, as well as serum VEGF-D, and quality of life assessment scores.

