## 6. Study Procedures and Timelines

### 6.1 Study and Timeline Overview

Patients will be identified by the medical and research staff at the LAM clinic at the University of Cincinnati Medical Center. Study staff will screen up to 60 patients over 15 months with a goal of enrolling 25 participants. Patients who meet eligibility criteria, provide informed consent and are enrolled in the study will receive instructions regarding resveratrol dosage, route and administration. An 8-week supply of resveratrol will be provided at visit 1. Patients will begin resveratrol at a starting dose of 250mg daily, and increase the dose in two increments to a maximum dose of 1000mg daily. If patients do not tolerate a certain dose of resveratrol, the dose will be reduced to the last tolerated strength. Patients will remain on the last well-tolerated dose of resveratrol for the entire study duration. Patients who are unable to tolerate the lowest dose of resveratrol will be withdrawn from study.

The patients will be given a copy of the informed consent form. Patients will be given ample time to read and discuss the consent form with the study staff. The study staff will then answer any remaining questions asked by the patients. The patients will be offered the option of signing the consent form. Those who agree to participate will undergo the remainder of screening visit.

Prior to starting study drug, pre/post bronchodilator spirometry, diffusion capacity of carbon monoxide (DLCO), and serum VEGF-D will be obtained to establish baseline values prior to study drug initiation. The best values for FEV1 and FVC obtained during the spirometry maneuvers will be used. Patients will be followed with serial spirometry and VEGF-D levels collected at the initial visit, followed by week 8, week 16 and week 24 visits. DLCO will also be obtained at the 24-week visit in addition to spirometry.

For patients who agree to the home spirometry study, we will teach them on the proper technique to perform, record and transmit home spirometry, and provide them with a home spirometer. The patients will perform their first test during the initial visit and we will use those values to compare the home spirometer values with the office-based spirometry values. After that patients will be instructed to perform home spirometry once a week as detailed in Section 5.7.

Section 6.2 provides a summary of the study timeline and procedures.

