## 6.2 Schedule of Events:

Event	Screening Visit*	Initial Visit	Week 2	Week 4	Week 8	Week 12	Week 16	Week 18	Week 20	Week 24
Visit number	0 or Phone	1	Lab check	Phone	2	Phone	3	Lab check	Phone	4
Informed consent	X									
History and physical		X			X		X			X
CBC, CMP		X			X		X			X
Lipid panel		X			X					X
Serum VEGF-D	X	X			X		X			X
Sirolimus level		X	X***	X***	X	X***	X	X***	X***	X
Urine Pregnancy Test**		X			X		X			
Saved serum and plasma		X			X		X			X
Spirometry post BD		X			X		X			X
Diffusion capacity		X								X
Home spirometry dispensed		X****								
Review concomitant meds		X		X	X	X	X		X	X
Review adverse events				X	X	X	X		X	X
SGRQ		X			X		X			X
ATAQ-LAM		X			X		X			X
EuroQOL		X			X		X			X
SD-SOB		X			X		X			X

Window for all visits after the initial visit:  $\pm 7$  days, except Weeks 2 and 18 where the window is  $\pm 3$  days

\* Screening visit can be the initial visit if a patient meets all inclusion/exclusion criteria. Informed consent for study inclusion can be obtained remotely over the phone rather than in-person. VEGF-D levels to confirm eligibility for trial participation can be drawn remotely rather than an in-person visit.

\*\* Only required for women of childbearing potential.

\*\*\* Can be drawn remotely. This is a trough level to be obtained  $24 \pm 4$  hours after the last sirolimus dose.

\*\*\*\* FEV1 and FVC will be obtained once weekly from patients agreeing to participate in the home spirometry sub study. Detailed instructions regarding the proper use of the home spirometer will be provided at the time of enrollment, along with access to detailed instruction manuals for future use. Once a week, patients will perform at least three spirometric measurements at approximately the same time, and record the best FEV1 and FVC values as their weekly results. These results, along with the associated flow-volume and volume-time loops will then be transmitted electronically to the study coordinator.

ATAQ-LAM: A Tool to Assess Quality of Life in LAM, BD: Bronchodilators, CBC: complete blood count, CMP: comprehensive metabolic panel, SGRQ: St. George's Respiratory Questionnaire, SD-SOB: San Diego Shortness of Breath scale, VEGF-D: Vascular Endothelial Growth Factor-D.

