**Home spirometry evaluation:** The spirometry values will be expressed as mean  $\pm$  SD. All spirometry maneuvers will be checked for acceptability and reproducibility as specified in the ATS/ERS criteria (38) by an expert pulmonary physiologist. The spirometry values obtained from maneuvers that do not satisfy the ATS/ERS criteria for acceptability will not be used in the primary analysis. If spirometric values meet the acceptability criteria but fail to satisfy the repeatability criteria, those values will be graded for quality, but will be used in the primary analysis. Overall compliance with weekly home spirometry will be recorded and reported as a percentage. Comparison of home spirometry and office-based spirometry values will be performed using the Bland-Altman method at baseline, and at each time frame that patients get an office-based spirometry (i.e. every 8 weeks). Rate of change of FEV1 (slope) over time will be calculated by using all available values (without imputations) in a linear mixed effects model after considering the correlation of the observations within each subject, and the time between measurements will be treated as a fixed effect. In order to analyze if the trends obtained from short-term follow up with frequent home spirometry correlate with overall disease trajectory, we will compare the rate of decline obtained after 8 weeks of home spirometry to the overall rate of decline obtained after 24 weeks of follow up. A similar analysis plan will be employed for serum VEGF-D, and other biomarkers. All statistical analyses for this study will be performed using SAS, version 9.4 (SAS Institute Cary NC).

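### The plan does not fix the bronchodilator state of office or home spirometry, so the home-versus-office Bland-Altman comparison can mix bronchodilator response with device bias

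*Combined protocol and SAP*

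**What the plan says.** Office spirometry is described in two ways.

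- **Pre and post bronchodilator.** Protocol Synopsis, Study Procedures: "Pre and post bronchodilator spirometry measurements will be performed at each visit". Section 6.1, for baseline: "Prior to starting study drug, pre/post bronchodilator spirometry, diffusion capacity of carbon monoxide (DLCO), and serum VEGF-D will be obtained". Section 8.2, first sentence: "Pre and post bronchodilator spirometry and DLCO measurement will be performed in a standardized manner".
- **Post bronchodilator.** Section 8.2, third sentence: "All PFTs obtained as part of the study will be performed post bronchodilator only, regardless of whether bronchodilator responsiveness is demonstrated". The Section 6.2 schedule has one spirometry row, "Spirometry post BD", and no pre-bronchodilator row. Section 6.3 states a post-bronchodilator rule for all visits and repeats it in the lists for weeks 8, 16 and 24.

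On the value to be analysed, Section 6.1 says only that the best FEV1 and FVC "obtained during the spirometry maneuvers will be used". It does not say whether these are pre or post.

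Home spirometry is described in the synopsis, Sections 5.7, 6.2, 6.3 and 8.5, and Section 15. None of these mentions a bronchodilator, either taken or withheld, or any record of recent use. The first home-device test is done in clinic: "The patients will perform their first test during the initial visit and we will use those values to compare the home spirometer values" (Section 6.1). Its order relative to the supervised bronchodilator is not given.

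The agreement analysis in Section 15 reads "Comparison of home spirometry and office-based spirometry values will be performed using the Bland-Altman method at baseline", and is repeated every eight weeks alongside office testing. Neither Section 15 nor the matching synopsis text names the office value that enters it.

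**The concern.** A Bland-Altman analysis attributes the mean difference and its spread to the two methods being compared. That holds only if both readings are taken under the same conditions. Here the operating instructions put the office reading after a bronchodilator and leave the home reading undefined. The lists for weeks 8, 16 and 24 include no home-device test in clinic, so the natural partner for the office value is a weekly home blow in an unknown bronchodilator state.

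Section 3.6 presents the substudy as validating home spirometry for LAM by direct comparison with laboratory testing. Section 3.3 lists bronchodilator responsiveness among the severity markers that track VEGF-D in LAM, so the response cannot be taken as zero or as equal across patients. If bronchodilator state is not recorded when the blows are made, the two components cannot be separated afterwards.

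**Working it through.** The plan states no figure on this point, so there is nothing to reproduce. The check is a reading of the text followed by an illustration under stated assumptions.

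**1. Which instruction governs in practice.** Staff work from the schedule and visit lists, and these consistently say post-bronchodilator. The pre-bronchodilator blow appears only in the synopsis, Section 6.1 and the first sentence of Section 8.2, and no analysis text uses it.

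**2. What the difference then contains.** For one patient at one visit,

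office − home = b + R × (1 − h) + noise,

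where b is device and setting bias, R is that patient's bronchodilator response, and h is 1 if the home blow was also taken after a bronchodilator and 0 if not. The documents do not fix h. The mean response therefore adds between nothing (all h = 1) and its full amount (all h = 0) to the apparent bias.

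**3. Inputs.** The documents give no response size and no device error. Assumed: mean response 0.05, 0.10 or 0.15 L; SD of response between patients 0.10 L; device bias 0; device SD 0.10 L; the two components independent; all h = 0, which is the worst case.

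**4. Limits of agreement** = bias ± 1.96 × SD of the differences.

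- Same bronchodilator state: SD 0.10 L, so 0 ± 1.96 × 0.10 = −0.20 to +0.20 L.
- Different state: SD = √(0.10² + 0.10²) = 0.141 L, and 1.96 × 0.141 = 0.277 L.

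| Assumed mean response (L) | Apparent bias (L) | Apparent limits (L) |
|---|---|---|
| matched blows | 0.00 | −0.20 to 0.20 |
| 0.05 | 0.05 | −0.23 to 0.33 |
| 0.10 | 0.10 | −0.18 to 0.38 |
| 0.15 | 0.15 | −0.13 to 0.43 |

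The mean response shifts the bias. The variation in response between patients widens the limits, from a half-width of 0.20 L to 0.28 L in this example.

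**5. A device fault can be hidden.** With a true device bias of −0.10 L and a mean response of 0.10 L, the apparent bias is −0.10 + 0.10 = 0.00 L.

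**6. What cancels.** Adding a constant to every office value leaves a correlation unchanged. A response that is stable within a patient drops out of that patient's change over time. The effect therefore falls mainly on absolute agreement.

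**7. Conditional effect on the home slope.** Suppose three things hold together: the visit-1 home blow follows the bronchodilator, later home blows do not, and the visit-1 blow enters the slope. In an ordinary least-squares slope on weekly points, the weight of week 0 is −(mean week)/Σ(week − mean)².

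- Weeks 0-8: −4/60 per week; × 100 mL × 52 = −347 mL/year per 100 mL of response, which is 347 × 8/52 ≈ 53 mL across the eight weeks.
- Weeks 0-24: −12/1300 per week; × 100 mL × 52 = −48 mL/year per 100 mL, which is 48 × 24/52 ≈ 22 mL across the 24 weeks.

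Section 15 plans a mixed model rather than least squares, so these figures indicate scale only. Section 15 also compares the 8-week rate with the 24-week rate, and the two would be affected unequally.

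**The case against.** The strongest reply is that practice is clearer than the text. The schedule and all visit lists agree on post-bronchodilator testing, so the pre-and-post wording may simply be left over. Office FEV1 and FVC changes would then be like for like across visits. The baseline comparison takes place in one clinic session, so if the home device is used after the same bronchodilator, that comparison is already matched. Home spirometry is an optional substudy. Section 3.5 calls an office-home bias of 0.20 L in a study of another disease slight, and the whole assumed range lies below that. The 150 mL limit in Section 5.7 concerns repeatability within a session, not bias between methods.

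Most of this stands, and it limits the reach of the point. It does not remove it. Consistent post-bronchodilator office testing is exactly what puts the response into the differences at weeks 8, 16 and 24, and the test order that would rescue the baseline comparison is not stated. The two yardsticks give scale only; neither shows that the shift is acceptable.

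Four stronger readings are tempting, and the documents do not support them.

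- A reader might infer that post-bronchodilator testing is an isolated statement in Section 8.2. It is the dominant operating instruction.
- A reader might infer that agreement is itself a secondary endpoint. Item 13 of Section 4.2 is a correlation, of absolute values and trends; Bland-Altman is an analysis in Section 15.
- A reader might infer that home blows are unmedicated. Their state is unspecified, and some patients may use their own inhaler first, so the added bias is up to the full response and not necessarily all of it.
- A reader might infer a false early decline in the home data. Section 6.1 gives the visit-1 home test the purpose of comparison with office values, with weekly testing starting afterwards. No text places that test after the bronchodilator or in the slope model.

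**Conclusion.** The point holds for absolute agreement. The sections contradict each other on office spirometry, the home state is undefined, and the Bland-Altman plan does not name the office value. Followed as the visit lists are written, the comparison at weeks 8, 16 and 24 estimates device and setting bias plus an unknown share of bronchodilator response, which may vary by patient. Under the assumed mean response of 50-150 mL, that adds up to 50-150 mL of apparent bias. The range is an assumption, not a figure from the documents.

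Correlation and within-patient trends are largely protected if the response is constant, and less so if it varies between patients or if home bronchodilator use changes from week to week. The slope figures apply only if all three conditions in step 7 of the working hold. The primary VEGF-D analysis is not affected. This should be corrected, but it does not threaten the trial's main conclusion.

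**What to change.** 1. Make the synopsis and Sections 6.1, 6.2, 6.3 and 8.2 give one description of office spirometry.
2. State in Section 15 and the synopsis that Bland-Altman compares blows in the same bronchodilator state, and name the values. One option is the pre-bronchodilator office blow, already promised at each visit in the synopsis, against home blows recorded as taken without recent bronchodilator. The other is home-device blows made in the same clinic session after the same bronchodilator as the office test.
3. Record bronchodilator use before each weekly home blow.
4. Fix the order of the visit-1 home test relative to the bronchodilator. If it comes after, leave that blow out of the home slope.

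The cost is wording changes, at most a few minutes of extra spirometry per visit, and one added item in the weekly home record.
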